## 2 Study Objectives

To determine if Ga-DOTATATE PET/CT imaging will have a similar accuracy as FDG PET/CT with NH3 in diagnosing CS and if it will be able to do so without the need for complex patient dietary preparation that is required with FDG PET/CT.

### 3 Study Design

The proposed investigation is a feasibility study designed to assess the efficacy of Ga-DOTATATE PET/CT imaging in the CS population. We propose imaging 15 consecutive patients initially (with an intention to do a larger study) with the standard of care approach of both FDG and NH3 PET/CT and a research Ga-DOTATATE PET/CT. The study group will include adult patients who undergo assessment in Mayo Clinic's CS clinic and have suspected or newly diagnosed CS based upon clinical evaluation. A typical proposed timeline of events for each patient processed through the study is as follows (note exact timeline may vary based on patient appointment schedule):

- 1) *Up to 4-6 weeks prior to visit:* Patient charts will be reviewed prior to their initial appointment in the CS clinic. After review, the physician head of the CS clinic (LB) will refer candidates that have clinically suspected (7), or newly diagnosed CS and who will be referred for a clinically indicated FDG and NH3 PET/CT to the primary investigator (JB). JB or other designated staff will contact the potential study candidates via phone or email (using a phone/email script) to determine their potential interest in the study. If the patient expresses an interest in the study, a consent form will be sent in advance for their review. Patients may consent remotely if they choose or can also be consented in-person. Potential study subjects will also be notified that they will be contacted during their visit for participation in the study.
- 2) *Day 1:* During their FDG and NH3 PET/CT assessment, potential study candidates who have not been consented will be approached by the study coordinator to inquire about their participation in the study. If the patient meets all criteria and agrees to participate in the study, then written consent will be obtained at that time.
- 4) *Day 2 or 3 (1-2 days after FDG and NH3 PET/CT):* Those study candidates who consent to the investigation will then undergo the study Ga-DOTATATE PET/CT scan. The patient will be provided with a brief survey at the end of their imaging session which will be conducted by the study coordinator to assess which protocol (if either) they preferred from a patient experience. Note patients will be allowed to complete the Ga-DOTATATE PET/CT study within a month of the FDG and NH3 PET/CT exam as long as no intervening immunomodulatory therapy has been administered.
- 5) Chart and imaging review will be conducted for each of the 15 patients in the study for purposes of drafting the study manuscript.

	Phone Introduction	Image Visit #1 FDG and NH3 PET/CT Imaging	Image Visit #2 Ga-DOTATATE PET/CT Imaging
Phone Introduction	X		
Clinically Indicated  FDG and  NH 3 PET/CT		X	

Research	 Ga-DOTATATE PET/CT			X
----------	----------------------------------	--	--	---

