After completion of both their FDG and NH3 and Ga-DOTATATE studies, a study coordinator will administer a patient survey regarding their experience with each protocol which will consist three questions. The first two question will ask the patient to rate the ease of undergoing each study on a 5 point scale (1=easiest, 5=harshest). The third question will ask the patient which study they preferred (FDG, Ga-DOTATATE or equal) with a comment section for why.

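### Ease of the FDG study is rated from memory after the DOTATATE scan, while DOTATATE is rated at once, so the endpoint 4 comparison carries a recall difference of unknown size and direction

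*Combined protocol and SAP*

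**What the plan says.** Section 3 (Study Design) sets out a typical timeline with the clinical FDG and ammonia scan on Day 1 and the research DOTATATE scan on Day 2 or 3. The DOTATATE scan may be done up to a month after the FDG scan if no immunomodulatory therapy intervenes. Inclusion criterion 4 (Section 4.1) repeats the one-month limit.

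The survey is described in two places:

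- Section 3, under the DOTATATE visit: "The patient will be provided with a brief survey at the end of their imaging session". The coordinator is named there as the person who runs it, and its stated aim is to learn which of the two protocols, if any, the patient liked better.
- Section 6.1.2 (Analysis of PET data): "After completion of both their" scans, "a study coordinator will administer a patient survey regarding their experience with each protocol which will consist three questions". Questions 1 and 2 rate the ease of each study from 1 (easiest) to 5 (harshest). On the last item: "The third question will ask the patient which study they preferred", with equal as a permitted answer.

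No rating at the FDG visit is described. Section 3.1 makes the comparison of patient satisfaction between the two protocols endpoint 4. Section 7 contains no analysis specific to the survey and no use of the interval between scans.

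**The concern.** The two ease ratings are meant to be compared, but they are not taken under the same conditions. In the described timeline, tracer, scan order and time since the experience all change together: FDG is first and remembered, DOTATATE is second and fresh. A difference in mean rating is then the sum of any real difference in burden, any recall effect and any contrast with the scan just finished. The data as planned hold nothing that could split that sum.

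The same role also recruits and collects the answers. On Day 1, "potential study candidates who have not been consented will be approached by the study coordinator", and the coordinator later conducts the survey about the research scan. Some patients may answer more kindly as a result.

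What is at stake is the size of the patient-experience difference. Better patient satisfaction is part of the rationale in Section 1.1, and endpoint 5 makes this pilot the basis for larger trials, so both the estimate and the way it was measured may be carried forward.

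**Working it through.** **Step 1: timing of each rating, from the text.**

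| | FDG ease (question 1) | DOTATATE ease (question 2) | Preference (question 3) |
|---|---|---|---|
| When asked | After both scans | After both scans | After both scans |
| Time since the scan, typical | 1-2 days | About 0 | Not applicable |
| Time since the scan, maximum | One month | About 0 | Not applicable |
| Must it wait for both scans? | No | No | Yes |

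Only question 3 needs both scans to be complete. The avoidable asymmetry lies in question 1 alone.

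**Step 2: can the analysis remove it?** Section 7.1.2.1 names a chi-square test, a two-sample t-test, univariate and multivariate analyses and a 0.05 threshold, without tying any of them to the survey. There is no FDG rating taken on the day, so the recall component cannot be estimated under any of these methods.

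**Step 3: how much could a shift matter?** The plan gives no effect size, SD or power for this endpoint, so there is no figure of its own to reproduce. What follows is an illustration.

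- From the documents: n = 15 (Section 3) and a 0.05 threshold (Section 7.1.2.1).
- Assumed: a two-sided paired t-test, no true difference, a systematic shift d of 0.25, 0.5 or 0.75 points, and an SD of the within-patient difference of 1 or 1.5.

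The noncentrality is d / SD × √15, with 14 degrees of freedom and a critical value of 2.145. For d = 0.5 and SD = 1 it is 0.5 × 3.873 = 1.936.

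| Shift (points) | SD 1: noncentrality | SD 1: chance of p<0.05 | SD 1.5: noncentrality | SD 1.5: chance of p<0.05 |
|---|---|---|---|---|
| 0 | 0 | 5% | 0 | 5% |
| 0.25 | 0.968 | 14.7% | 0.645 | 9.3% |
| 0.5 | 1.936 | 43.8% | 1.291 | 22.6% |
| 0.75 | 2.905 | 77.1% | 1.936 | 43.8% |

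**Step 4: dependence on the test.** If the two-sample t-test named in the plan were applied to the same data (SD of the difference 1, correlation 0.5 between a patient's two ratings), simulation gives about 4%, 20% and 52% for the three shifts, and 0.8% with no shift. The percentages therefore depend on the test as well as on the SD.

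**The case against.** The strongest reply has four parts.

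- **The planned gap is short.** It is 1-2 days, and a month is only an allowance, so most patients should remember the FDG preparation well. This stands. A reader might infer that recall over a month is the norm, but Section 3 presents it as the exception.
- **The direction is not shown.** A reader might infer that every patient is pushed towards DOTATATE. The documents do not support that. Fading memory of the diet could make FDG seem easier, contrast with a simpler scan could make it seem harder, and the two may partly cancel.
- **The mode is unclear.** A reader might infer an oral interview. Section 3 has the patient provided with a survey that the coordinator conducts, and Section 6.1.2 has the coordinator administer it. Either wording is compatible with a form that the patient fills in, so courtesy to the coordinator is a possibility only.
- **One sitting has a merit.** Rating both scans together gives a common reference frame, and the preference question has to come last anyway. This also stands, and it is a reason to add an FDG rating on the day instead of simply moving question 1.

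It can also be said that a scenario with no true difference sits badly with Section 1.2.1.5, which describes the FDG preparation as burdensome. That is fair. The scenario isolates the effect of a shift and is not a forecast. If a real difference exists, the same shift distorts its estimated size.

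None of this removes the asymmetry itself, which is plain in both sections.

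**Conclusion.** The point holds as a minor, avoidable weakness of endpoint 4. In the described timeline DOTATATE ease is rated at once and FDG ease from memory, typically after 1-2 days and at most after a month. Any resulting shift cannot be separated afterwards from a real difference.

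Its size and direction are unknown. The range of about 9% to 77% false-positive findings covers assumed shifts of 0.25 to 0.75 points, SDs of 1 and 1.5, and a paired t-test that the plan does not specify. It shows how sensitive 15 pairs are to a modest shift and should not be read as the error rate of this study. With a gap of 1-2 days the real shift may be small.

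The preference question is correctly timed. Concordance, sensitivity and specificity are not touched.

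**What to change.** 1. Have every consented patient complete the FDG ease question on a short form at the end of the FDG visit. State in advance that this is the FDG rating used in the endpoint 4 comparison.
2. Keep the three-question survey after the DOTATATE scan, so that the side-by-side ratings and the preference item are retained. The change between a patient's two FDG ratings then gives a direct look at recall and contrast combined.
3. Have patients fill in both forms themselves, and say so in the same words in Sections 3 and 6.1.2.
4. Record the number of days between scans.

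The cost is one extra form at a clinical visit. Consent must be signed first. Section 3 allows remote consent beforehand or written consent on Day 1, so this is feasible. A reader might assume that the coordinator already sees everyone on Day 1, but that contact is described only for patients not yet consented. Someone must be assigned to hand the form to those who consented remotely.

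The change does not remove the scan order of the described timeline or the lack of blinding of patients, and DOTATATE would still be rated with the FDG experience in mind. The report should state this.

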### **3.1 Study Endpoints**

1. Assess utilizing both qualitative and quantitative methods the myocardial Ga-DOTATATE uptake in patients with and without active CS as determined by FDG and NH3 PET/CT.
2. Determine the concordance and discordance of Ga-DOTATATE with FDG and NH3 PET/CT for the presence or absence of CS utilizing FDG and NH3 PET/CT as the “gold-standard” for CS. Determine the sensitivity and specificity of Ga-DOTATATE for the detection of CS will be determined.
3. Calculate physician confidence in study interpretation for both Ga-DOTATATE and FDG and NH3 PET/CT.
4. Compare patient satisfaction between the FDG and NH3 PET/CT and Ga-DOTATATE protocols.
5. Utilize information obtained from the current pilot as a foundation to pursue potentially larger trials.

## **4 Subject Selection and Withdrawal**

### **4.1 Inclusion Criteria**

- 1) 18 years of age or older
- 2) Referred for and undergo clinically indicated FDG PET/CT scan for CS
- 3) Have clinically suspected, or newly diagnosed CS
- 4) Are able to complete both the clinically indicated FDG and NH3 PET/CT and the Ga-DOTATATE scan and do so within one month of each other without the introduction of CS directed therapy between the scans

### **4.2 Exclusion Criteria**

- 1) Pregnant or nursing
- 2) Unable or unwilling to give consent for Ga-DOTATATE PET/CT scan
- 3) Are on an active immunosuppressive/immunomodulatory therapy

### **4.3 Early Withdrawal of Subjects**

#### **4.3.1 When and How to Withdraw Subjects**

The criteria for enrollment must be followed explicitly. If a subject who does not meet enrollment criteria is inadvertently enrolled, that subject should be discontinued from the study. A subject may voluntarily discontinue participation in this study at any time. The investigator may also, at his or her discretion, discontinue the subject from participating in this study at any time. If a subject is prematurely discontinued from participation in the study for any reason, at any time, at either the investigator's discretion or the subject's request, an effort must be made to document the reason(s) why a subject fails to return to the study clinic for necessary visits or is discontinued from the study. The primary reason for discontinuing participation in the study must be stated and may include, but is not limited to, one of the following:

- ◆ Occurrence of intolerable adverse events
- ◆ Withdrawal of consent for imaging by patient
- ◆ Noncompliance with protocol, e.g., the patient fails to appear at one or more imaging procedures
- ◆ Development of an intercurrent illness, injury, or medical condition likely to interfere with subject safety, the overall assessment, or the required administration of study medication
- ◆ Pregnancy
- ◆ Development of any condition for which the investigator feels treatment withdrawal is justified
- ◆ Termination of the study

Subjects withdrawn from the study will not be replaced, regardless of the reason for withdrawal.

An effort must be made to determine why a subject fails to return for the necessary visits or is dropped from the study.

## **5 Study Procedures**

### **5.1 Informed Consent**

The investigator will provide for the protection of the subjects by following all applicable regulations. The IRB must review the informed consent form used during the informed consent process.

Before any procedures specified in this protocol are performed, a subject must:

- Be informed of all pertinent aspects of the study and all elements of informed consent.
- Be given time to ask questions and time to consider the decision to participate.
- Voluntarily agree to participate in the study.
- Sign and date an IRB/IEC-approved informed consent form.

(If a procedure is done routinely as standard of care, then it is not study-specific, and it may be done before the consent is signed.)

## 6 Methods

### 6.1 PET/CT Imaging

#### 6.1.1 PET/CT Imaging Protocol

A GE Discovery 690XT, Discovery Molecular Insights (DMI) or 710 PET/CT system (GE Healthcare, Waukesha, WI) will be utilized in performing the studies. The imaging system consists of full ring Cerium-doped Lutetium Yttrium Orthosilicate (LYSO) crystals. 128x128 PET matrix size with zoomed 41.9 cm field of view centered over the heart will be used to obtain the PET images. Furthermore, three-dimensional list mode acquisition will be employed. Three-dimensional iterative reconstruction algorithm with time-of-flight correction, CT attenuation, scatter, randoms, normalization, decay and dead time correction will be utilized. Three-dimensional Hanning post-filter with a 10 mm cut-off will also be used.

A 64 slice-spiral CT will be employed with auto exposure control with modulated current in order to maintain consistent noise index (noise index set at 33 with mA range 10-180). For our CT attenuation imaging tube ration is 0.5 s, KV is 120 and pitch is 0.98. Slice thickness is 3.75 mm and slice increment is 3.27 mm. Matrix size is 512 x 21.

As per all of our clinical FDG PET/CT CS studies NH3 will be administered to optimize diagnostic accuracy for CS. This same perfusion map will be used for the Ga-DOTATAE imaging portion (no additional ammonia N-13 will be given for the Ga-DOTATATE study).

#### 6.1.2 Analysis of PET data

Once the cardiac PET/CT images are obtained they will be assessed for the presence of CS utilizing similar methodologies which were previously published (1,2,24).

Qualitative assessment of FDG and NH3 PET/CT and Ga-DOTATATE for each study subject will be made by two different study investigators (JB and AK) who will be blinded to the patient clinical history, laboratory data and any other imaging assessment (including the corresponding CS study-i.e. when reading the Ga-DOTATATE study investigators will be blinded to the FDG results and vice versa) at the time of interpretation. For both FDG and Ga-DOTATATE cardiac uptake study investigators will classify the patient into one of four categories of radionuclide uptake: none, diffuse, focal, and focal on diffuse or diffuse. The portions of the myocardium that demonstrate uptake will be documented in accordance with the 17 segment American Heart Association model (28). In concordance with national guidelines(24), FDG and Ga-DOTATATE examinations will be interpreted simultaneously with NH3 to allow for assessment of myocardial perfusion. Both FDG and Ga-DOTATATE studies will then be labeled as positive for CS, negative for CS or inconclusive.

Any discordance between the findings of the two investigators in regards to the presence or absence of CS as well as the extent will be reviewed by additional investigators (GJ or PC) and final determination in regards to classification of the patient will be made.

Semiquantitative determination of radionuclide uptake will be determined by using commercially available software to calculate maximum standard uptake value (SUVmax) of FDG and Ga-DOTATATE in the heart. This data will be correlated with patient clinical data obtained from the medical record.

The two study investigators (JB and AK) who are reviewing all studies will rank their confidence level for interpretation for each scan on a 5 point scale (1=least confident, 5= most confident). Results will then be compared between the two study modalities.

After completion of both their FDG and NH3 and Ga-DOTATATE studies, a study coordinator will administer a patient survey regarding their experience with each protocol which will consist three questions. The first two question will ask the patient to rate the ease of undergoing each study on a 5 point scale (1=easiest, 5=harshest). The third question will ask the patient which study they preferred (FDG, Ga-DOTATATE or equal) with a comment section for why.

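### The blind is not secured as written: one blinded reader receives the referrals, and the adjudicators of disputed reads are not stated to be blinded

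*Combined protocol and SAP*

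**What the plan says.** All references are to the combined protocol and SAP.

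- **Readers.** Section 6.1.2 names two investigators by initials to read both studies of every patient, "blinded to the patient clinical history, laboratory data and any other imaging assessment". It adds that "study investigators will be blinded to the" FDG result when they read the DOTATATE scan, and the reverse. The blind applies at the time of interpretation. Each scan is labelled positive, negative or inconclusive.
- **Adjudication.** If the two readers differ on presence, absence or extent of cardiac sarcoidosis (CS), the case "will be reviewed by additional investigators", again named by initials, and a final classification of the patient is made. Nothing is said about what these people may see.
- **Referral.** In Section 3, step 1, the head of the CS clinic, after chart review, "will refer candidates that have clinically suspected (7), or newly diagnosed CS" to the primary investigator. That investigator "or other designated staff will contact the potential study candidates via phone or email". The initials given for the primary investigator are those of one of the two blinded readers.
- **Shared image.** Section 6.1.1 reuses the ammonia perfusion map from the clinical study for the DOTATATE study. Section 6.1.2 has it read together with each tracer.
- **Use of the labels.** They feed endpoint 2 in Section 3.1 and the concordance, sensitivity and specificity analysis in Section 7.1.2.1. The two readers' confidence scores feed endpoint 3.

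**The concern.** In an agreement study the index and reference labels must be reached independently. If the same person sees both scans, or carries the same clinical information into both reads, errors in the two labels become correlated. Observed agreement can then exceed what the tracer would achieve alone. Sensitivity and specificity are affected in the same way, because the FDG/ammonia label is the reference.

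Two gaps leave room for this. The people who decide the disputed reads are outside the blinding clause. And one person inside it has a recruitment role that brings clinical information and possibly patient contact. Section 3.1 offers the pilot as the foundation for larger trials, so an optimistic agreement figure would carry forward. Calls made with knowledge of the other scan cannot be made independent afterwards.

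**Working it through.** The plan gives no agreement target, power calculation or adjudication rate, so there is no figure of its own to reproduce. The check is mainly a comparison of the text, followed by a sense of scale.

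**1. Referral role against reader role.** Section 3 sends the referrals to the primary investigator. Handing over patient contact to other staff is optional, and it would not redirect the referral itself. Section 6.1.2 requires the same person to be blind to clinical history. No step separates the two roles.

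**2. Reach of the blinding clause.** It is attached to the two readers. The adjudication paragraph follows it and states no blind. It speaks of classifying the patient rather than a scan, so opening both tracers together is permitted.

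**3. Support for the cross-tracer blind.** The text gives no coding of scans, reading order or interval between a patient's two reads. It does not say who reads the clinical FDG scan for care. The ammonia map is common to both reads, so in a 15-patient series a reader could recognise the patient. Coding alone will not remove that.

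**4. Value of one label.** With N = 15 (Section 3), one changed positive/negative label moves concordance by 1/15 = 6.7 points. Sensitivity and specificity have smaller denominators, since reference positives and negatives share at most 15 patients, so one label moves them by more.

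**5. Precision.** Exact (Clopper-Pearson) 95% intervals:

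| Concordant | Estimate | 95% CI |
|---|---|---|
| 12/15 | 80.0% | 51.9 to 95.7 |
| 13/15 | 86.7% | 59.5 to 98.3 |
| 14/15 | 93.3% | 68.1 to 99.8 |
| 15/15 | 100% | 78.2 to 100 |

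**6. Illustration, adjudication route (all inputs assumed).** Let *d* be the share of DOTATATE scans adjudicated, *a* the agreement with FDG of a blinded adjudicator on those scans, and *k* the share of the remaining disagreements pulled to the FDG label when the adjudicator sees it. The expected rise in concordance is *d* × *k* × (1 − *a*).

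- Low: 0.1 × 0.25 × (1 − 0.7) = 0.0075, about 0.8 points, or 15 × 0.0075 = 0.1 patients.
- High: 0.3 × 1 × (1 − 0.6) = 0.12, that is 12.0 points, or 15 × 0.12 = 1.8 patients.

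**7. Illustration, reader route (all inputs assumed).** If true agreement is *A* and a share *s* of discordant reads is pulled to the FDG label, the rise is *s* × (1 − *A*).

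- Low: 0.1 × (1 − 0.9) = 1 point, or 15 × 0.01 = 0.15 patients.
- High: 0.5 × (1 − 0.7) = 15 points, or 15 × 0.15 = 2.25 patients.

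Steps 6 and 7 show that inflation is possible. They do not show that it will occur.

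**The case against.** The strongest reply is that the safeguard most relevant to agreement is already written: both readers are blind to the other tracer, in both directions. Receiving a referral does not breach that. The referral may come 4-6 weeks before the visit, before either scan exists. Suspected or newly diagnosed CS is itself an inclusion criterion (Section 4.1), so the category separates patients little and reveals neither result. Coded images read later would satisfy the clause. All of this stands, and it limits the referral concern to a role conflict that the plan should resolve.

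Three stronger readings are tempting, and the documents do not support them.

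- *The adjudicators are unblinded.* The text is silent; it states neither that they are blinded nor that they are not. Likewise it states no reading order, which is not the same as a fixed one.
- *One reader knows each patient's clinical status.* The text shows receipt of referrals. It does not show that this reader reviews the chart.
- *A large part of the result is biased.* If 2 to 4 of 15 patients went to adjudication (an assumption), that would be 2/15 = 13.3% to 4/15 = 26.7% of patients. This is a share decided under an unspecified blind, not an estimate of inflation. Disputes about extent, recorded over 17 segments, also trigger adjudication and need not change a positive/negative label.

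Disputes may also be few. Section 1.2.1.5 cites a 19-patient study with 100% inter-observer agreement on the somatostatin-tracer read, although that figure does not cover FDG reads. The adjudication gap does not touch the confidence comparison, since only the two primary readers score confidence; recognition through the shared ammonia map could.

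Finally, this is a feasibility pilot, and random order and separate sessions are good practice rather than corrections of an error. That is fair, but the text as written still permits joint adjudication with both scans and the chart open.

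**Conclusion.** The point holds in a limited form: the blind is not secured as written. One reader's recruitment role conflicts with the required blinding to clinical history, and those who settle disputed reads are not stated to be blinded to the chart or the other tracer. Agreement, sensitivity and specificity could be inflated as a result.

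The size cannot be derived from the documents. The only firm figure is 6.7 points of concordance per changed label with all 15 patients counted. The illustrative rises (0.8 to 12.0 points by adjudication, 1 to 15 by reader knowledge) rest entirely on assumed inputs.

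A reader might infer that the blind fails outright. The documents do not support that, because cross-tracer blinding of the two primary readers is explicit; what is missing is the procedure that would protect it. The change should be made because it is cheap and must be in place before the scans are read.

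**What to change.** 1. Apply the blinding sentence of Section 6.1.2 to the adjudicators, and have each tracer adjudicated on its own, without the other tracer or the chart.
2. In Section 3, route referrals and patient contact to the coordinator or designated staff who are not readers.
3. Read coded scans in random order, with a patient's two tracers in separate sessions. Because the ammonia map is common to both reads, recognition may not be removed completely, and the report should say so.
4. Keep each reader's pre-adjudication call, and report concordance, sensitivity and specificity from those calls as a sensitivity analysis.

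The cost is protocol wording, coordinator time to code and shuffle 15 × 2 = 30 tracer studies, and slightly later results because reads are batched. No new readers are needed. If the team already intends these safeguards, only the wording has to be added.
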